7.1.5 Visit Requirements

Visit requirements are outlined in [Section 6.0](#) – Study Calendar. Specific procedure-related details are provided in [Section 7.1](#) – Trial Procedures.

7.1.5.1 Screening

Within 21 days prior to start of treatment, potential subjects will be evaluated to determine that they fulfill the entry requirements as set forth in [Section 5.1](#). Screening procedures may be repeated after consultation with the Sponsor.

Results of a test performed prior to the subject signing consent as part of routine clinical management are acceptable in lieu of a screening test if performed within the specified time frame. Screening procedures are to be completed within 21 days prior to the first dose trial treatment except for the following:

Laboratory tests and ECOG PS are to be performed within 10 days prior to the first dose of trial treatment.

For women of reproductive potential, a urine pregnancy test will be performed within 72 hours prior to the first dose of trial treatment. A serum test may be considered if urine test is not appropriate or inconclusive.

Subjects may be rescreened after initially failing to meet the inclusion/exclusion criteria. Results from assessments performed during the initial screening period are acceptable in lieu of a repeat screening test if performed within the specified time frame and the inclusion/exclusion criteria is met. Subjects who are rescreened will retain their original screening number.

7.1.5.2 Treatment Period

Visit requirements are outlined in [Section 6.0](#) – Study Calendar. Specific procedure-related details are provided in [Section 7.1](#) – Trial Procedures.

7.1.5.3 Post-Treatment Visits

7.1.5.3.1 Safety Follow-Up Visit

The mandatory Safety Follow-Up Visit should be conducted approximately 30 days after the last dose of trial treatment or before the initiation of a new anti-cancer treatment, whichever comes first. All AEs that occur prior to the Safety Follow-Up Visit should be recorded. Subjects with an AE of Grade > 1 will be followed until the resolution of the AE to Grade 0-1 or until the beginning of a new anti-neoplastic therapy, whichever occurs first. SAEs that occur within 90 days of the end of treatment or before initiation of a new anti-cancer treatment should also be followed and recorded. Subjects who are eligible for retreatment with pembrolizumab (as described in [Section 7.1.5.5](#)) may have up to two safety follow-up visits, one after the Treatment Period and one after the Second Course Phase.

7.1.5.4 Follow-up Visits

Subjects who discontinue trial treatment for a reason other than disease progression will move into the Follow-Up Phase and should be assessed every 6 weeks (42 ± 7 days) by radiologic imaging to monitor disease status. After 1 year, the imaging time point will occur every 9 weeks (± 7 days). Every effort should be made to collect information regarding disease status until the start of new anti-neoplastic therapy, disease progression, death, end of the study or if the subject begins retreatment with pembrolizumab as detailed in [Section 7.1.5.5](#). Information regarding post-study anti-neoplastic treatment will be collected if new treatment is initiated.

Subjects who are eligible to receive retreatment with pembrolizumab according to the criteria in [Section 7.1.5.5](#) will move from the follow-up phase to the Second Course Phase when they experience disease progression. Details are provided in [Section 6.2](#) – Second Course Phase.

7.1.5.4.1 Survival Follow-up

Once a subject experiences confirmed disease progression or starts a new anti-cancer therapy, the subject moves into the survival follow-up phase and should be contacted by telephone every 12 weeks to assess for survival status until death, withdrawal of consent, or the end of the study, whichever occurs first.

7.1.5.5 Second Course Phase (Retreatment Period)

Subjects who stop pembrolizumab with SD or better may be eligible for up to one year of additional pembrolizumab therapy if they progress after stopping study treatment. A repeat course of palliative radiotherapy to the primary tumor will not be given during this time. This retreatment is termed the Second Course Phase of this study and is only available if the study remains open and the subject meets the following conditions:

- **Either**
 - Stopped initial treatment with pembrolizumab after attaining an investigator-determined confirmed CR according to RECIST 1.1, and
 - Was treated for at least 24 weeks with pembrolizumab before discontinuing therapy
 - Received at least two treatments with pembrolizumab beyond the date when the initial CR was declared

OR

- Had SD, PR or CR and stopped pembrolizumab treatment after 24 months of study therapy for reasons other than disease progression or intolerance

AND

- Experienced an investigator-determined confirmed radiographic disease progression after stopping their initial treatment with pembrolizumab
- Did not receive any anti-cancer treatment since the last dose of pembrolizumab
- Has a performance status of 0 or 1 on the ECOG Performance Scale
- Demonstrates adequate organ function as detailed in [Section 5.1.1](#)
- Female subject of childbearing potential should have a negative urine or serum pregnancy test within 72 hours prior to receiving retreatment with study medication.
- Female subject of childbearing potential should be willing to use 2 methods of birth control or be surgically sterile, or abstain from heterosexual activity for the course of the study through 120 days after the last dose of study medication (Reference Section 5.5.2). Subjects of child bearing potential are those who have not been surgically sterilized or have been free from menses for > 1 year.

- Male subject should agree to use an adequate method of contraception starting with the first dose of study therapy through 120 days after the last dose of study therapy.
- Does not have a history or current evidence of any condition, therapy, or laboratory abnormality that might interfere with the subject's participation for the full duration of the trial or is not in the best interest of the subject to participate, in the opinion of the treating investigator.

Subjects who restart treatment will be retreated at the same dose and dose interval as when they last received pembrolizumab. Patients will not receive another course of palliative radiotherapy to their primary tumor. Treatment will be administered for up to one additional year.

Visit requirements are outlined in [Section 6.2](#) – Second Course Phase.

8.0 DATA AND SAFETY MONITORING PLAN

8.1 Definition of Risk Level

This is a Risk Level 4 study as defined in the [City of Hope Institutional Data and Safety Monitoring Plan](#) [policy dated 07/09/2014]. This determination was made because the study is an investigator-initiated phase II trial and involves a COH IND.

8.2 Monitoring and Personnel Responsible for Monitoring

The Protocol Management Team (PMT) is responsible for monitoring the data and safety of this study. The PMT consists of the Principal Investigator (PI), Biostatistician, Research Protocol Nurse, and Clinical Research Coordinator.

The PMT is required to submit periodic status reports (i.e., the PMT Report) according to the frequency prescribed in the [City of Hope Institutional Data and Safety Monitoring Plan](#) [policy dated 07/09/2014]. Important decisions made during PMT meetings (i.e., dose escalation, de-escalation, etc.) only need to be noted in the PMT Report submitted to the Data and Safety Monitoring Committee (DSMC).

8.3 Adverse Events and Serious Adverse Events

The PI will be responsible for determining the event name, assessing the severity (i.e., grade), expectedness, and attribution of all adverse events.

Adverse Event (AE) - An adverse event is any untoward medical experience or change of an existing condition that occurs during or after treatment, whether or not it is considered to be related to the protocol intervention.

Reporting Non-serious Adverse Events – Adverse events will be collected after the patient is given the study treatment or any study related procedures. Adverse events will be monitored by the PMT. Adverse events that do not meet the criteria of serious OR are not unanticipated problems will be reported only in the PMT Report.

Serious Adverse Event (SAE) [Modified from the definition of unexpected adverse drug experience in [21 CFR 312.32](#)] - defined as *any expected or unexpected adverse events* that result in any of the following outcomes:

- Death
- Is life-threatening experience (places the subject at immediate risk of death from the event as it occurred)
- Unplanned hospitalization (equal to or greater than 24 hours) or prolongation of existing hospitalization
- A persistent or significant disability/incapacity
- A congenital anomaly/birth defect
- Secondary malignancy
- Any other adverse event that, based upon appropriate medical judgment, may jeopardize the subject's health and may require medical or surgical intervention to prevent one of the outcomes listed above (examples of such events include allergic bronchospasm requiring intensive treatment in the emergency room or at home, blood dyscrasias or convulsions that do not result in inpatient hospitalization, or the development of drug dependency or drug abuse).

Reporting Serious Adverse Events - begins after study treatment or any study related procedures. All SAEs occurring during this study, whether observed by the physician, nurse, or reported by the patient, will be reported according to the approved [City of Hope's Institutional policy](#) [policy effective date: 05/14/14]. Serious Adverse Events that require expedited reporting will be submitted electronically using [iRIS](#).

Adverse Event Name and Severity

The PI will determine the adverse event name and severity (grade) by using the CTCAE version 4.0.

Expected Adverse Event - Any event that does not meet the criteria for an unexpected event, OR is an expected natural progression of any underlying disease, disorder, condition, or predisposed risk factor of the research participant experiencing the adverse event.

Unexpected Adverse Event [[21 CFR 312.32 \(a\)](#)] – An adverse event is unexpected if it is not listed in the investigator's brochure and/or package insert; is not listed at the specificity or severity that has been observed; is not consistent with the risk information described in the protocol and/or consent; is not an expected natural progression of any underlying disease,

disorder, condition, or predisposed risk factor of the research participant experiencing the adverse event.

Adverse Event Attribution

The following definitions will be used to determine the causality (attribution) of the event to the study agent or study procedure.

Definite - The AE is clearly related to the investigational agent or study procedure and unrelated to any other cause.

Probable - The AE is likely related to the investigational agent or study procedure and unlikely related to other cause(s).

Possible - The AE may be related to the investigational agent or study procedure and may be related to another cause(s).

Unlikely - The AE is doubtfully related to the investigational agent or study procedure and likely related to another cause(s).

Unrelated - The AE is clearly not related to the investigational agent or study procedure and is attributable to another cause(s).

COH Held IND

Serious Adverse Events meeting the requirements for expedited reporting to the Food and Drug Administration (FDA), as defined in [21 CFR 312.32](#), will be reported as an IND safety report using the [MedWatch Form FDA 3500A for Mandatory Reporting](#).

The criteria that require reporting using the Medwatch 3500A are:

- Any unexpected fatal or life threatening adverse experience associated with use of the drug must be reported to the FDA no later than 7 calendar days after initial receipt of the information [[21 CFR 312.32\(c\)\(2\)](#)]
- Any adverse experience associated with use of the drug that is both serious and unexpected must be submitted no later than 15 calendar days after initial receipt of the information [[21 CFR 312.32\(c\)\(1\)](#)]
- Any follow-up information to a study report shall be reported as soon as the relevant information becomes available. [[21 CFR 312.32\(d\)\(3\)](#)]

The PI or designee will be responsible for contacting the Office of IND Development and Regulatory Affairs (OIDRA) at COH to ensure prompt reporting of safety reports to the FDA. OIDRA will assist the PI with the preparation of the report and submit the report to the FDA

in accordance with the approved [City of Hope's Institutional policy](#) [policy effective date: 05/14/14].

8.4 Deviations and Unanticipated Problems

Deviation - A deviation is a divergence from a specific element of a protocol that occurred without prior IRB approval. Investigators may deviate from the protocol to eliminate immediate hazard(s) for the protection, safety, and well-being of the study subjects without prior IRB approval. For any such deviation, the PI will notify the COH DSMC and IRB within 5 calendar days of its occurrence via [iRIS](#) in accordance with the [Clinical Research Protocol Deviation policy](#) [policy effective date: 11/07/11].

Single Subject Exception (SSE)

An SSE is a planned deviation, meaning that it involves circumstances in which the specific procedures called for in a protocol are not in the best interests of a specific patient. It is a deviation that is anticipated and receives prior approval by the PI and the IRB. The SSE must be submitted as a “Single Subject Exception Amendment Request” via [iRIS](#) in accordance with IRB guidelines and the [Clinical Research Protocol Deviation policy](#) [policy effective date: 11/07/11]. An IRB approved SSE does not need to be submitted as a deviation to the DSMC.

Unanticipated Problem (UP) – Any incident, experience, or outcome that meets all three of the following criteria:

1. Unexpected (in terms of nature, severity, or frequency) given the following: a) the research procedures described in the protocol-related documents such as the IRB approved research protocol, informed consent document or Investigator Brochure (IB); and b) the characteristics of the subject population being studied; **AND**
2. Related or possibly related to participation in the research (possibly related means there is a reasonable possibility that the incident, experience, or outcomes may have been caused by the drugs, devices or procedures involved in the research); **AND**
3. Suggests that the research places subjects or others at greater risk of harm (including physical, psychological, economic, or social harm) than previously known or recognized.

Any UP that occurs during study conduct will be reported to the DSMC and IRB in accordance with the [City of Hope's Institutional policy](#) [policy effective date: 05/14/14] using [iRIS](#).

8.5 Definition of an Overdose for This Protocol and Reporting of Overdose to Merck

For purposes of this trial, an overdose of pembrolizumab will be defined as any dose of 1,000 mg or greater (≥ 5 times the indicated dose). No specific information is available on the treatment of overdose of pembrolizumab. Appropriate supportive treatment should be provided if clinically indicated. In the event of overdose, the subject should be observed closely for signs of toxicity. Appropriate supportive treatment should be provided if clinically indicated.

If an adverse event(s) is associated with (“results from”) the overdose of a Merck product, the adverse event(s) is reported as a serious adverse event, even if no other seriousness criteria are met.

If a dose of Merck’s product meeting the protocol definition of overdose is taken without any associated clinical symptoms or abnormal laboratory results, the overdose is reported as a non-serious Event of Clinical Interest (ECI), using the terminology “accidental or intentional overdose without adverse effect.”

All reports of overdose with and without an adverse event must be reported within 2 working days hours to Merck Global Safety. (Attn: Worldwide Product Safety; [contact])

8.6 Reporting of Pregnancy and Lactation to Merck

Although pregnancy and lactation are not considered adverse events, it is the responsibility of investigators or their designees to report any pregnancy or lactation in a subject (spontaneously reported to them), including the pregnancy of a male subject's female partner that occurs during the trial or within 120 days of completing the trial completing the trial, or 30 days following cessation of treatment if the subject initiates new anticancer therapy, whichever is earlier. All subjects and female partners of male subjects who become pregnant must be followed to the completion/termination of the pregnancy. Pregnancy outcomes of spontaneous abortion, missed abortion, benign hydatidiform mole, blighted ovum, fetal death, intrauterine death, miscarriage and stillbirth must be reported as serious events (Important Medical Events). If the pregnancy continues to term, the outcome (health of infant) must also be reported.

Such events must be reported within 2 working days to Merck Global Safety. (Attn: Worldwide Product Safety; [contact])

8.7 Reporting of Adverse Events to Merck

8.7.1.1 Serious Adverse Events

A serious adverse event is any adverse event occurring at any dose or during any use of Merck’s product that:

- Results in death;
- Is life threatening;
- Results in persistent or significant disability/incapacity;
- Results in or prolongs an existing inpatient hospitalization;
- Is a congenital anomaly/birth defect;
- Is a new cancer (that is not a condition of the study);
- Is associated with an overdose;
- Is another important medical event

Any serious adverse event, or follow up to a serious adverse event, including death due to any cause other than progression of the cancer under study that occurs to any subject from the time the consent is signed through 90 days following cessation of treatment, or the initiation of new anti-cancer therapy, whichever is earlier, whether or not related to Merck product, must be reported within 24 hours to Merck Global Safety.

Non-serious Events of Clinical Interest will be forwarded to Merck Global Safety and will be handled in the same manner as SAEs.

Additionally, any serious adverse event, considered by an investigator who is a qualified physician to be related to Merck product that is brought to the attention of the investigator at any time outside of the time period specified in the previous paragraph also must be reported immediately to the Sponsor and to Merck.

SAE reports and any other relevant safety information are to be forwarded to the Merck Global Safety [contact]

A copy of all 15 Day Reports and Annual Progress Reports is submitted as required by FDA, European Union (EU), Pharmaceutical and Medical Devices agency (PMDA) or other local regulators. Investigators will cross reference this submission according to local regulations to the Merck Investigational Compound Number (IND, CSA, etc.) at the time of submission. Additionally investigators will submit a copy of these reports to Merck & Co., Inc. (Attn: Worldwide Product Safety; [contact]) at the time of submission to FDA.

All subjects with serious adverse events must be followed up for outcome.

9.0 STATISTICAL ANALYSIS PLAN

9.1 Primary Objective

The primary objective of this study is to establish that the combination of pembrolizumab and a palliative course of traditional external beam multifractionated RT in patients with metastatic gastric, esophageal, and/or GEJ cancers will lead to an increase in tumor infiltrating cytotoxic T-cells and circulating cytotoxic T cells and a reduction in immunosuppressive Tregs and MDSCs in non-irradiated sites.

Each patient will serve as their own control, and tumor cytotoxic T cell infiltration and immunosuppressive Tregs will be compared pre- and post-treatment. As variability of the difference in the T cell populations pre- and post-treatment is unknown and still being established, the power calculation is based on the concept of “effect size” in this biomarker analysis study. Specifically, a sample-size of 14 patients will have 80% power to detect an effect size of 0.71 using a paired t-test with a 0.05 one-sided significance level. The effect size is the mean difference divided by the standard deviation of the difference.

A positive biological signal combined with acceptable secondary endpoints (response and toxicity) are sought for a clear indication of promise of this combination.

9.2 Secondary Objectives

Secondary objectives such as ORR per RECIST 1.1 and irRECIST, PFS, and OS are exploratory, though will also be documented, along with toxicity. All patients who receive at least one dose of pembrolizumab will be included in the safety analysis. Stool/oral microbiomic profiling and germline miRNA biomarker panel analyses will also be correlated with secondary outcome measures of ORR and toxicities.

While overlapping toxicities are not anticipated with the combination of pembrolizumab and RT, the initial treatment of patients within this trial warrants a careful review of toxicity:

- **Toxicity-based Interim Analysis:** A study hold will be placed for re-evaluation at the proposed starting dose as accrual proceeds on this phase II study according to the following rule: The study will hold pending an amendment if 3 patients discontinue therapy after cycle 1 due to treatment-related toxicity. This rule has a 97% chance of holding the study if the true discontinuation rate due to toxicity on cycle 1 is 50%. It has a 15% chance of holding if the true discontinuation rate on cycle 1 is 15%.
- **Treatment-related mortality stopping rule:** Any treatment-related death will hold the study accrual pending review by the PI, Sponsor, and DSMB/IRB.

With 14 patients, there is 96% power to detect at least one responder if the true response rate is 21% or higher, which is in the range of 22% in the phase I trial of pembrolizumab among gastric cancer patients with PD-L1 overexpression. As a result, failure to observe any response in the 14 patients would result in lack of enthusiasm for the combination of pembrolizumab and RT in this patient population. PFS and OS will be determined using the Kaplan-Meier method.

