2.0 TRIAL DESIGN

2.1 Trial Design

This is a single-arm, prospective, phase II, biomarker analysis trial of pembrolizumab in combination with palliative radiotherapy for patients with metastatic squamous cell or adenocarcinoma of the esophagus, stomach, or gastroesophageal junction (GEJ). We will enroll 14 patients within our institution who are in need of palliative radiation for symptoms related to their primary tumor including pain, dysphagia, and bleeding. Patients with a single metastatic site in need of palliative radiation (e.g., pain from a bony metastasis, enlarged lymph nodes, liver metastasis, etc.) will also be eligible provided they have other measurable metastatic sites outside of the radiation field. The exception will be patients who require palliative radiation to a symptomatic central nervous system (CNS) metastasis. The first dose of palliative radiation and first dose of pembrolizumab will commence on cycle 1, day 1.

Participation in this trial will be dependent on patients having a metastatic site amenable to ultrasound and/or CT-guided biopsy, inclusive of patients with malignant ascites amenable to ultrasound-guided aspiration, and agreeing to provide pre- and post-treatment biopsies for the

IRB Protocol No. 16099

Version: 04

[figure not shown]
Version Date: 10/16/2019

biomarker analysis primary endpoint of the study. Patients who are undergoing palliative radiation for a single target metastatic site, and only the primary tumor is amenable to biopsy are also eligible to participate if they consent to endoscopic pre- and post-treatment biopsies.

Treatment will continue until documented clinical PD, unacceptable AE(s), intercurrent illness that prevents further administration of treatment, investigator's decision to withdraw the patient, patient withdraws consent, pregnancy of the subject, noncompliance with trial treatment or procedure requirements, completion of 35 administrations (approximately 2 years) of treatment with study medication or achievement of a complete response.

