5.2 Trial Treatments

The treatment to be used in this trial is outlined below in [Table 1](#).

Table 1 Trial Treatment

Drug	Dose/Potency	Dose Frequency	Route of Administration	Regimen/Treatment Period	Use
Pembrolizumab	200 mg	Q3W	IV infusion	Day 1 of each 3 week cycle	Experimental
Radiotherapy	3 Gy	Daily	External Beam	Daily except weekends and holidays for 10 fractions	Standard of care and combination agent

Trial treatment should begin as close as possible to the date on which treatment is allocated/assigned. The first dose of pembrolizumab on cycle 1, day 1 should occur on the same day after the first fraction of radiation therapy.

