5.2.1.2 Dose Modification

Adverse events (both non-serious and serious) associated with pembrolizumab exposure may represent an immunologic etiology. These adverse events may occur shortly after the first dose or several months after the last dose of treatment. Pembrolizumab must be withheld for drug-related toxicities and severe or life-threatening AEs as per [Table 2](#) below. See [Section 5.4.1](#) and Events of Clinical Interest Guidance Document for supportive care guidelines, including use of corticosteroids.

Table 2: Dose Modification Guidelines for Drug-Related Adverse Event

Toxicity	Hold Treatment For Grade	Timing for Restarting Treatment	Discontinue Subject
Diarrhea/Colitis	2-3	Toxicity resolves to Grade 0-1.	Toxicity does not resolve within 12 weeks of last dose or inability to reduce corticosteroid to 10 mg or less of prednisone or equivalent per day within 12 weeks.
	4	Permanently discontinue	Permanently discontinue
AST, ALT, or Increased Bilirubin	2	Toxicity resolves to Grade 0-1	Toxicity does not resolve within 12 weeks of last dose.
	3-4	Permanently discontinue (see exception below) ¹	Permanently discontinue
Type 1 diabetes mellitus (if new onset) or Hyperglycemia	T1DM or 3-4	Hold pembrolizumab for new onset Type 1 diabetes mellitus or Grade 3-4 hyperglycemia associated with evidence of beta cell failure.	Resume pembrolizumab when patients are clinically and metabolically stable.
Hypophysitis	2-3	Toxicity resolves to Grade 0-1	Toxicity does not resolve within 12 weeks of last dose or inability to reduce corticosteroid to 10 mg or less of prednisone or equivalent per day within 12 weeks.
	4	Permanently discontinue	Permanently discontinue
Hyperthyroidism	3	Toxicity resolves to Grade 0-1	Toxicity does not resolve within 12 weeks of last dose or inability to reduce corticosteroid to 10 mg or less of prednisone or equivalent per day within 12 weeks.
	4	Permanently discontinue	Permanently discontinue
Hypothyroidism	2-4	Therapy with pembrolizumab can be continued while treatment for the thyroid disorder is instituted	Therapy with pembrolizumab can be continued while treatment for the thyroid disorder is instituted.
Infusion Reaction	3-4	Permanently discontinue	Permanently discontinue
Pneumonitis	2	Toxicity resolves to Grade 0-1	Toxicity does not resolve within 12 weeks of last dose or inability to reduce corticosteroid to 10 mg or less of prednisone or equivalent per day within 12 weeks.
	3-4	Permanently discontinue	Permanently discontinue

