a.	Patients will continue pembrolizumab for a maximum of 35 cycles for first course of therapy if no evidence of disease progression or intolerable toxicity.													
b.	In patients who discontinue study therapy without documented disease progression, every effort should be made to continue monitoring disease status by radiologic imaging every 6 weeks (± 7 days) until 1) the start of new anti-cancer treatment, 2) disease progression on imaging, 3) death, or 4) the end of the study, whichever occurs first.													
c.	After the start of new anti-cancer treatment or documented disease progression by imaging, the patient should be contacted by telephone every 12 weeks to assess for survival status.													
d.	Laboratory tests and ECOG PS are to be performed within 10 days prior to the first dose of trial treatment.													
e.	Palliative radiotherapy to a total dose of 30 Gy to the primary tumor will be delivered in 3 Gy fractions daily with the exception of weekends and holidays. The first fraction of radiation should be given on C1D1 prior to administration of pembrolizumab. Radiation may continue into cycle 2 if delayed for management of toxicity or administrative reasons.													
f.	For women of reproductive potential, a urine pregnancy test will be performed within 72 hours prior to the first dose of trial treatment. A serum test may be considered if urine test is not appropriate or inconclusive.													
g.	Thyroid function tests should be collected at screening and every 6 weeks in concordance with day 1 of even-numbered cycles.													
h.	Serum CEA should be collected at screening and every 6 weeks in concordance with day 1 of odd-numbered cycles.													
i.	Tumor imaging should be performed every 6 weeks through the first 6 cycles, then subsequently performed every 9 weeks thereafter. For patients who complete 35 cycles of therapy or 2 years of follow up without evidence of progression, scans can be spaced out to every 12-24 weeks at the discretion of the treating physician. The exception will be patients who demonstrate PD, PR, or CR by RECIST 1.1, in which event the next imaging will be performed at 6 weeks for confirmation. Refer to Section 7.1.2.6.2 for details.													

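### The toxicity hold rule in Section 9.2 fits neither its own operating figures nor the discontinuation timing in Table 2, and probably leaves non-fatal toxicity from cycle 2 on without a numeric boundary

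*Combined protocol and SAP*

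**What the plan says.** Section 9.2 (toxicity-based interim analysis) sets the hold: "The study will hold pending an amendment if 3 patients discontinue therapy after cycle 1 due to treatment-related toxicity". It then gives two operating figures, both tied to the rate in cycle 1: "This rule has a 97% chance of holding the study if the true discontinuation rate due to toxicity on cycle 1 is 50"%, and "It has a 15% chance of holding if the true discontinuation rate on cycle 1 is 15"%. Section 2.1 fixes the sample size: "We will enroll 14 patients within our institution". Table 1 in Section 5.2 sets the cycle length: "Day 1 of each 3 week cycle".

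Table 2 in Section 5.2.1.2 governs when toxicity ends treatment. For many held Grade 2-3 toxicities the discontinuation criterion is "Toxicity does not resolve within 12 weeks of last dose", in most rows with an alternative criterion about steroid tapering over the same period. The same section says of pembrolizumab adverse events: "These adverse events may occur shortly after the first dose or several months after the last dose of treatment". Section 5.2.3.5 lists late radiation effects. Footnote e of the Section 6.1 calendar adds: "Radiation may continue into cycle 2 if delayed for management of toxicity or administrative reasons".

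Three other safeguards have no cycle limit: the accrual hold for any treatment-related death (Section 9.2), criterion 3 for early termination (Section 5.7), and monitoring by the protocol management team with reports to the data and safety monitoring committee (Section 8.2).

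**The concern.** Three parts of the plan describe the monitored event differently. The rule counts discontinuations *after cycle 1*, which could mean at the end of cycle 1 or at any later time. The operating figures are for discontinuation *on cycle 1*. Table 2 often defers the discontinuation decision well past day 21. The figures make the cycle 1 reading the better supported one.

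On that reading there are two consequences. A toxicity that starts in cycle 1 and is held may become a discontinuation only after cycle 1 has closed, and Section 9.2 does not say whether or when it is then counted, or how the patient is treated while the hold is pending. A non-fatal toxicity discontinuation that arises in cycle 2 or later is not counted, although first-course treatment may run to 35 administrations. Where radiation is delayed into cycle 2, even the combined exposure is incomplete when the window closes.

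At stake is the trial's one numeric boundary for non-fatal toxicity. Its stated hold probabilities say nothing about later discontinuations, and a team applying the rule could not tell from the text which patients to count.

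**Working it through.** **Inputs.** n = 14 (Section 2.1); threshold 3, stated probabilities 97% at 50% and 15% at 15% (Section 9.2); cycle of 3 weeks (Table 1); hold of up to 12 weeks from last dose (Table 2); accrual of 24 months (Section 1.0). The share of discontinuations arising in cycle 1 is not in the documents and is assumed below.

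**1. The plan's own figures.** With X ~ Binomial(14, p), the chance of a hold at threshold r is P(X ≥ r) = 1 − Σ C(14,k) p^k (1−p)^(14−k), summed over k = 0 to r−1.

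| Threshold | p = 50% (stated 97%) | p = 15% (stated 15%) |
|---|---|---|
| 3 of 14 | 99.4% | 35.2% |
| 4 of 14 | 97.1% | 14.7% |

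For example, at p = 15% and r = 3: 1 − (0.1028 + 0.2539 + 0.2912) = 0.352. Subtracting P(X = 3) = 0.2056 gives 0.147 for r = 4. With threshold 3, no n from 8 to 14 gives both stated figures: n = 11 gives 96.7% and 22.1%, and n = 9 gives 91.0% and 14.1%. The stated pair fits 4 or more of 14, not the written 3.

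**2. Delay from a hold begun in cycle 1.** If the only dose is on day 1 of cycle 1, the 12-week limit falls 12 − 3 = 9 weeks after cycle 1 ends. Accrual is 14/24 = 0.583 patients per month. Nine weeks is 2.07 months, so 0.583 × 2.07 = 1.2 further patients could enrol before the event is declared. Over the full 12 weeks (2.76 months) it is 1.6, but the first 3 of those weeks lie inside cycle 1.

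**3. Discontinuations arising from cycle 2 on.** Let the true overall rate of treatment-related discontinuation be q and the assumed cycle 1 share be f. On the cycle 1 reading, the rule sees p = f × q. For q = 30%, f = 1/3 gives p = 10% and f = 2/3 gives p = 20%. For q = 40%, the values are 13.3% and 26.7%.

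| Overall rate q | Threshold | f = 1/3 | f = 2/3 | All counted (f = 1) |
|---|---|---|---|---|
| 30% | 3 of 14 | 16% | 55% | 84% |
| 30% | 4 of 14 | 4% | 30% | 64% |
| 40% | 3 of 14 | 28% | 76% | 96% |
| 40% | 4 of 14 | 11% | 54% | 88% |

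The last column assumes that every discontinuation among the 14 is known in time to act on it. It is therefore an upper limit for any rule that works only while accrual is open.

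**The case against.** The strongest reply is that a short early window is a legitimate design choice. Section 9.2 presents the rule as a check on initial treatment at the starting dose, and ten weekday fractions normally finish inside cycle 1. Table 2 requires immediate permanent discontinuation for many Grade 3-4 events, including pneumonitis, hepatic (with a stated exception), renal and infusion reactions, so these reach the count without the 12-week wait if they occur in cycle 1. A patient held from cycle 1 who never restarts can still be counted, so the hold mainly delays the count. Later harm is not unwatched, given the death hold, the early-termination criterion and committee review. The safety analysis also covers every patient who receives a dose of pembrolizumab, so the final judgement on toxicity does not depend on the hold rule.

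Most of this stands, and it limits the point. A reader might infer that much of the harm never reaches the rule. The documents do not support that: they say events may occur late, and give no timing distribution. Nor do they settle that events from cycle 2 on are never counted, because the wording of the rule also admits a broad reading. And this is not the trial's only safety threshold, since a single treatment-related death also holds accrual.

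What the reply does not remove is the mismatch. None of the other safeguards is a numeric boundary for non-fatal toxicity. If the broad reading was intended, the stated probabilities describe a different event from the one counted. On either reading the written threshold does not produce them.

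**Conclusion.** The point holds as an inconsistency that should be corrected. The rule, its operating figures and Table 2 do not describe the same event, and the threshold of 3 does not yield the stated 97% and 15%. The threshold mismatch is plain arithmetic and needs no assumption beyond independent patients and n = 14.

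The coverage gap depends on the cycle 1 reading, which the operating figures favour but the wording does not fix. Its size depends on an assumed cycle 1 share of one third to two thirds. At a true overall rate of 30%, the hold probability would be 16% to 55% with a threshold of 3, or 4% to 30% with a threshold of 4, against at most 84% or 64% if all discontinuations counted. The delay is modest: up to about 9 weeks beyond cycle 1, or about 1.2 patients, and only for toxicities that take the full hold before discontinuation.

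**What to change.** Revise Section 9.2 so that it agrees with Table 2:

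- Define the counted event as a treatment-related discontinuation declared at any time while accrual is open, including one that follows a hold begun in cycle 1.
- State how a patient on a pending Table 2 hold is counted until the hold resolves. One option is a provisional event, removed if treatment resumes.
- Reconcile the threshold with the operating figures. Whether 3 or 4 was meant is for the study team to say.
- Restate the hold probabilities for the event as defined, with the assumed timing of discontinuations.

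The 90-day window for serious adverse events should not be used to bound the count: it begins when treatment stops, so no discontinuation can fall inside it.

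Table 2 and the management of individual patients stay as they are. The cost is a change of wording and a running count from data the team already collects. The downside is more holds for review at acceptable toxicity rates, because a wider event counts more patients. If the true rate of the newly defined event were 15%, the chance of a hold would be up to 35% with a threshold of 3 and 15% with a threshold of 4.
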